8 ADVERSE EVENTS

8.1 Definition of Adverse Events

As defined by the ICH/GCP (CPMP/ICH/135/95), an AE is:

- Any untoward medical occurrence in a study patient administered a pharmaceutical product and which does not necessarily have a causal relationship with this treatment.
- An AE can therefore be any unfavorable and unintended sign (including an abnormal laboratory finding), symptom, or disease temporally associated with the use of a medicinal product, whether or not considered related to the medicinal product.

An AE includes but is not limited to:

- Any clinically significant worsening of a patient's pre-existent condition
- An overdose, whether accidental or deliberate, defined as a dose higher than that prescribed by a healthcare professional for clinical reasons, or a dose higher than that described in the approved labelling for a marketed product, or in available clinical data for a study drug
- Abuse (i.e., use for nonmedical reasons) of an investigational or marketed product

Note: Progression of the cancer under study is not considered an adverse event.

A protocol-related AE is any AE that bears a direct relationship to a study procedure or the alteration of ongoing pre-study drug regimens, medical procedures, or treatments discontinued as required by the protocol.

8.1.1 *Recording and Reporting of Adverse Events*

All adverse events that occur after the consent form is signed but before treatment start must be reported by the investigator if they cause the subject to be excluded from the study, or are the result of a protocol-specified intervention, including but not limited to washout or discontinuation of usual therapy, diet, placebo treatment or a procedure.

From the time of treatment start through 30 days following cessation of treatment, all adverse events must be reported by the investigator. Such events will be recorded at each examination on the Adverse Event case report forms/worksheets. The reporting timeframe for adverse events meeting any serious criteria is described in section Immediate Reporting of Adverse Events to the Sponsor. The investigator will make every attempt to follow all subjects with non-serious adverse events for outcome.

AEs will be reported in accordance with the NCI CTCAE v4.03, using a recognized medical term or diagnosis that accurately reflects the event. AEs will be assessed by the Investigator for severity and relationship to investigational product (birinapant/pembrolizumab), for other possible etiologies, and whether the event meets criteria as an SAE and therefore requires immediate notification to the Sponsor. If an AE has not resolved at the end of the study reporting period, it will be documented as ongoing. If an AE evolves into a condition that becomes “serious,” it will be reported as an SAE.

For hematological toxicity fluctuations, record the highest grade during the cycle on the patient’s eCRF.

8.1.2 Severity of an Adverse Event

Severity of AEs will be graded according to NCI CTCAE version 4.03.

AEs that are not included in the NCI CTCAE lists will be graded according to the NCI CTCAE general guideline for grades as follows:

- Grade 1** Mild, asymptomatic or mild symptoms; clinical or diagnostic observations only; intervention not indicated.
- Grade 2** Moderate, minimal, local intervention, or noninvasive intervention indicated; limiting age-appropriate instrumental activities of daily living (ADL), e.g., preparing meals, shopping for groceries or clothes, using the telephone, managing money.
- Grade 3** Severe or medically significant but not immediately life-threatening; hospitalization or prolongation of hospitalization indicated; disabling; limiting self-care ADL, e.g., bathing, dressing and undressing, feeding self, using the toilet, taking medications, and not bedridden.
- Grade 4** Life-threatening consequences; urgent intervention indicated.
- Grade 5** Death related to adverse event

8.1.3 Relationship of an Adverse Event

Causal relationship to study drug will be rated as follows:

- **Not Related** –
 - A medical condition that is present before the administration of study drug unless the condition worsens or episodes increase in frequency after administration of investigational product;
 - Symptoms that are reasonably determined to be the normal course of the disease state (NOTE: life-threatening complications from cancer are considered SAEs);
 - An event for which sufficient information exists to indicate the etiology is related to a concomitant medication;

- Medical events (e.g., unrelated illness, accident, or trauma) that occur during the clinical study for which sufficient information exists to indicate that the etiology is not related to the investigational product;
- Symptoms from procedures such as surgery or radiation which are not a direct result of receiving investigational product.
- **Possibly Related –**
 - An event that follows a reasonable temporal sequence from administration of the investigational product;
 - An event that follows a known or expected response pattern to the suspected investigational product but could readily have been produced by a number of other factors.
- **Probably Related -**
 - An event that follows a reasonable temporal sequence from investigational product administration;
 - An event that follows a known or expected response pattern to the suspected investigational product;
 - Is confirmed by stopping or reducing the dosage of the investigational product;
 - Cannot be reasonably explained by the known characteristics of the patient's clinical state or by other factors.
- **Definitely Related -**
 - An event that follows a reasonable temporal sequence from investigational product administration;
 - Follows a known or expected response pattern to the suspected investigational product;
 - Is confirmed by improvement on stopping or reducing the dosage of the investigational product and reappearance of the reaction on repeated exposure unless the latter is considered to be medically unethical.

Certain drug-mediated AEs and laboratory abnormalities may not resolve promptly upon dechallenge. While dechallenge-rechallenge may afford the Investigator greater confidence regarding causality of an AE, the welfare and consent of the patient must be primary in any decision to rechallenge with discontinued investigational product. In the absence of rechallenge, the Investigator will use his/her best judgment and consider all available information when determining the most likely relationship between the AE and investigational product treatment.

The designee CRO pharmacovigilance physician will review AE attribution independently. This is not a conclusive determination of causal association between the investigational product and the event. Whenever the Investigator's assessment is

unknown or unclear, the AE will be treated as investigational product-related for the purposes of reporting to regulatory authorities.

8.2 Serious Adverse Events

8.2.1 Definition of a Serious Adverse Event

A SAE is an AE that results in any of the following outcomes:

- Results in death
- Is life threatening (i.e. the patient is at immediate risk of death at the time the event occurred; it does not refer to an event which might hypothetically have caused death had it been more severe)
- Requires in-patient hospitalization or prolongation of existing hospitalization
- Results in persistent or significant disability/incapacity
- Is a congenital anomaly/birth defect
- Other (medically important) events that may not result in death, be life-threatening, or require hospitalization may be considered serious when, based upon appropriate medical judgment, they may jeopardize the patient and may require medical or surgical intervention to prevent one of the outcomes listed in this definition. Examples include allergic bronchospasm requiring intensive treatment in an emergency room or at home, blood dyscrasias or convulsions that do not result in in-patient hospitalization, or the development of drug dependency or drug abuse.

If there is any doubt whether the AE constitutes an SAE, it should be treated as serious and reported as such, until confirmation can be obtained.

8.2.2 Expectedness

An AE is considered unexpected if it has not been described previously in either published descriptions of the investigational product (e.g., package inserts), in the medical literature, or in reports of previous clinical trials of the investigational product, including the IB.

8.3 Notification/Reporting of a Serious Adverse Event

In addition to the criteria listed in [Section 8.2.1](#), adverse events meeting either of the below criteria, although not serious per ICH definition, are reportable to the Sponsor in the same timeframe as SAEs to meet certain local requirements.

Therefore, these events are considered serious by the Sponsor for collection purposes, if they are.

- A new cancer (that is not a part of the cancer being studied); or
- Associated with an overdose.

For the time period beginning when the consent form is signed until treatment start, any serious adverse event, or follow up to a serious adverse event, including death due to any cause other than progression of the cancer under study (refer to [Section 9.1](#) for additional details), that occurs to any subject must be reported within 24 hours to the Sponsor if it causes the subject to be excluded from the study, or is the result of a protocol-specified intervention, including but not limited to washout or discontinuation of usual therapy, diet, placebo treatment or a procedure.

For the time period beginning at treatment start through 90 days following cessation of treatment, or 30 days following cessation of treatment if the subject initiates new anticancer therapy, whichever is earlier, any serious adverse event, or follow up to a serious adverse event, including death due to any cause other than progression of the cancer under study (refer to [Section 9.1](#) for additional details), whether or not related to the Sponsor's product, must be reported within 24 hours to the Sponsor by paper.. Paper reporting procedures can be found in the Investigator Trial File Binder (or equivalent)

Additionally, any serious adverse event, considered by an investigator who is a qualified physician to be related to the Sponsor's product that is brought to the attention of the investigator at any time following consent through the end of the specified safety follow-up period specified in the paragraph above, or at any time outside of the time period specified in the previous paragraph also must be reported immediately to the Sponsor.

After submitting an initial SAE report for a patient, the Investigator is required to follow the patient proactively and provide further information on the patient's condition to Diamond PV Services Ltd.

	Diamond PV Services Ltd
Central Email	[contact]
[contact]

All subjects with SAEs should be followed to resolution or stabilization by the Investigator or until 30 days after the last dose of any investigational product. All related SAEs should continue to be followed, even if this extends beyond the study reporting period. Resolution of an SAE is defined as the return to baseline status or stabilization of the condition with the expectation that it will remain chronic.

To the Institutional Review Board

In addition to reporting the SAE to the Sponsor or representative, the Investigator must also notify the IRB which approved the study according to their requirements.

Copies of all correspondence relating to reporting of any SAEs should be maintained in the site's study files and will be checked routinely by the Study Monitor.

8.4 Notification of Events of Clinical Interest

Selected non-serious and serious adverse events are also known as Events of Clinical Interest (ECI) and must be reported to the Sponsor.

Events of clinical interest for this study include:

1. An overdose of Sponsor's product, as defined for pembrolizumab as ≥ 1000 mg (5 times the dose) and for birinapant as any dose $\geq 15\%$ greater than the protocol assigned cohort dose that may or may not be associated with clinical symptoms or abnormal laboratory results. No specific information is available on the treatment of overdose of pembrolizumab or birinapant. In the event of overdose, the subject should be observed closely for signs of toxicity. Appropriate supportive treatment should be provided if clinically indicated.
2. An elevated AST or ALT lab value that is greater than or equal to 3X the upper limit of normal and an elevated total bilirubin lab value that is greater than or equal to 2X the upper limit of normal and, at the same time, an alkaline phosphatase lab value that is less than 2X the upper limit of normal, as determined by way of protocol-specified laboratory testing or unscheduled laboratory testing. Corresponding redacted local laboratory report must be sent in with the SAE reporting form.

The purpose of the criteria is to specify a threshold of abnormal hepatic tests that may require an additional evaluation for an underlying etiology. The trial site guidance for assessment and follow up of these criteria can be found in the Investigator Trial File Binder (or equivalent).

3. A cranial nerve palsy

For the time period beginning when the consent form is signed until treatment start, any ECI, or follow up to an ECI, that occurs to any subject must be reported within 24 hours to the Sponsor if it causes the subject to be excluded from the study, or is the result of a protocol-specified intervention, including but not limited to washout or discontinuation of usual therapy, diet, placebo treatment or a procedure.

For the time period beginning at treatment start through 30 days following cessation of treatment, any ECI, or follow up to an ECI, whether or not related to the Sponsor's product, must be reported within 24 hours to the Sponsor, by paper. Paper reporting procedures can be found in the Investigator Trial File Binder (or equivalent).

8.5 Withdrawal Due to an Adverse Event

Any patient who experiences an AE may be withdrawn from investigational product treatment and/or the study at any time, at the discretion of the Investigator. If a patient is withdrawn wholly or in part because of an AE, both the AE page and termination page (end of treatment termination and/or study termination) of the CRF will be completed at that time, especially if the patient may not be able to return to the investigative site for the regularly scheduled follow-up visit.

The patient's condition will be monitored until the event has resolved or stabilized, until the patient is referred to the care of a health care professional, or until a determination of a cause unrelated to the study drug or study procedure is made.

8.6 Pregnancy

Based on information solicited by the Investigator at scheduled study follow-up or provided spontaneously by patients at any time, if a patient becomes pregnant or the partner of a male patient participating in the study becomes pregnant during the study or within 3 months of discontinuing the investigational product (birinapant/pembrolizumab), the Investigator will report the pregnancy to Diamond PV Services Ltd within 24 hours. If treatment with investigational product is ongoing at the time, the investigational product will be immediately discontinued for any female patient who becomes pregnant.

The female patient or the partner of a male patient should be followed at least monthly by the Investigator and the subject's status documented until the pregnancy has been completed or terminated. The outcome of the pregnancy will be reported to the Sponsor without delay and within 24 hours if the outcome is a serious adverse experience (e.g., death, abortion, congenital anomaly, or other disabling or life-threatening complication to the mother or newborn). The study investigator will make every effort to obtain permission to follow the outcome of the pregnancy and report the condition of the fetus or newborn to the Sponsor. If the pregnancy ends for any reason before the anticipated date, the Investigator will attempt to determine the cause and will notify the Sponsor. At the completion of the pregnancy, the Investigator will document the outcome of the pregnancy. If the outcome of the pregnancy meets the criteria for immediate classification as an SAE (i.e. postpartum complication, spontaneous abortion, stillbirth, neonatal death, or congenital anomaly) the Investigator will pregnancy will be reported to the Sponsor without delay and within 24 hours if the outcome is a serious adverse experience (e.g., death, abortion, congenital anomaly, or other disabling or life-threatening complication to the mother or newborn). The study investigator will make every effort to obtain permission to follow the outcome of the pregnancy and report the condition of the fetus or newborn to the Sponsor.

8.6.1 Reporting of Pregnancy and Lactation to the Sponsor

Although pregnancy and lactation are not considered adverse events, it is the responsibility of investigators or their designees to report any pregnancy or lactation in a subject (spontaneously reported to them) that occurs during the study.

Pregnancies and lactations that occur after the consent form is signed but before treatment start must be reported by the investigator if they cause the subject to be excluded from the study, or are the result of a protocol-specified intervention, including but not limited to washout or discontinuation of usual therapy, diet, placebo treatment or a procedure.

Pregnancies and lactations that occur from the time of treatment start through 120 days following cessation of Sponsor's product, or 30 days following cessation of treatment if the subject initiates new anticancer therapy, whichever is earlier, must be reported by the investigator. All reported pregnancies must be followed to the completion/termination of the pregnancy. Pregnancy outcomes of spontaneous abortion, missed abortion, benign hydatidiform mole, blighted ovum, fetal death, intrauterine death, miscarriage and stillbirth must be reported as serious events (Important Medical Events). If the pregnancy continues to term, the outcome (health of infant) must also be reported.

Such events must be reported within 24 hours to the Sponsor by paper. Paper reporting procedures can be found in the Investigator Trial File Binder (or equivalent).

9 EFFICACY

Although the clinical benefit of the combination of these drug(s) has not yet been established, the intent of offering this treatment is to provide a possible therapeutic benefit, and thus the patient will be carefully monitored for tumor response and symptom relief in addition to safety and tolerability. Patients with measurable disease will be assessed using RECIST v 1.1 and iRECIST (Seymour et al. 2017). For the purposes of this study, all patients will be required to have a CT scan of their chest, abdomen, and pelvis within 28 days of Cycle 1 Day 1 and then will be re-evaluated every 9 weeks (end of every 3rd treatment cycle). The same radiological imaging modality used at screening must be used throughout the patient's course of treatment (CT or MRI; X-ray is not adequate to assess measurable disease). In the event of a response, a confirmatory scan must be performed 4 weeks following initial assessment of response.

9.1 Antitumor Effect

Response and progression will be evaluated in this study using Response Evaluation Criteria in Solid Tumors (RECIST) guideline version 1.1. and iRECIST.

9.1.1 *Tumor Imaging*

Tumor imaging should be performed by computed tomography (CT) (preferred). MRI should only be used when CT is contraindicated or for imaging in the brain, but the same imaging technique should be used in a patient throughout the study. An MRI can be utilized if clinically appropriate. X-ray may not be used to assess disease.

All patients are required to have a CT of the chest, abdomen, and pelvis within 28 days of Cycle 1 Day 1. Local site study team reading (Investigator assessment with site radiology reading) based on RECIST 1.1 and iRECIST will be used to determine patient eligibility and response.

Scans performed as part of routine clinical management are acceptable for use as initial tumor imaging if they are of diagnostic quality and performed within 28 days before Cycle 1 Day 1.

9.1.2 **RECIST 1.1 Response Criteria**

Table 9 Disease Response Criteria for Target and Non-Target Lesions

Category	Response Criteria	
	Target Lesions	Non-Target Lesions
Complete Response (CR)	Disappearance of all target lesions. Any pathological lymph nodes (target or non-target) must have reduction in short axis to < 10mm.	Disappearance of all non-target lesions. All lymph nodes must be non-pathological in size (< 10mm short axis).
Partial Response (PR)	A \geq 30% decrease in the sum of the longest diameter of target lesions, taking as reference the baseline sum longest diameter	N/A
Non-CR/Non PD	N/A	Persistence of one or more non-target lesion(s).
Not Evaluable	When no imagining/measurement is done at a particular time-point or if only a subset of lesions is made at an assessment.	When no imagining/measurement is done at a particular time-point or if only a subset of lesions is made at an assessment.
Stable Disease (SD)	Neither sufficient shrinkage to qualify for PR nor sufficient increase to qualify for PD, taking as reference the smallest sum longest diameter since treatment started.	N/A
Progressive Disease (PD)	A \geq 20% increase in the sum of the longest diameter of target lesions, taking as reference the smallest sum longest diameter recorded since the treatment started, or the appearance of one or more new lesions.	Appearance of one or more new lesions, and/or unequivocal progression of existing non-target lesions.

Source: (Eisenhauer et al. 2009).

Table 10 Time Point Response: Patients with Target (+/- Non-Target) Disease

Target Lesions	Non-Target Lesions	New Lesions	Overall Response
CR	CR	No	CR
CR	Non CR/Non-PD	No	PR
CR	Not Evaluated	No	PR
PR	Non-PD or Not all Evaluated	No	PR
SD	Non-PD or Not all Evaluated	No	SD
Not All Evaluated	Non-PD	NO	NE
PD	Any	Yes or NO	PD
Any	PD	Yes or NO	PD
Any	Any	Yes	PD

CR=complete response, PR=partial response, SD=stable disease, PD=progressive disease, and NE=not evaluated

Source: (Eisenhauer et al. 2009).

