9.1.2.2 Lesions that split or grow together

If a target lesion splits into two separate lesions, the lesion diameters need to be added together to calculate the sum of the lesions. If two target lesions grow together, the vector of the longest diameter of the now merged lesions will be recorded as the lesion measurement.

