In patients who have initial evidence of radiological PD, it is at the discretion of the treating physician whether to continue a patient on study treatment until repeat imaging is obtained. This clinical judgment decision should be based on the patient's overall clinical condition, including performance status, clinical symptoms, and laboratory data.

iRECIST criteria include the above RECIST 1.1 derived criteria (see Table 11 and Table 12 below) with the proviso that the increase in tumor burden must be shown to increase, but in the case of iUSD, iUPR or iCR, the assessment time bar is reset.

For target lesions, iCR, iPR and iSD can all be assigned after iUPD has been documented as long as iCPD has not been confirmed. Progression is confirmed in the target lesion category if the next imaging assessment after iUPD (4-8 weeks later) confirms an increase in the sum of target lesions dimensions of greater than 5 mm. However, iCPD is not met if the imaging assessment after iUPD is followed by CR, PR or SD (compared to baseline as defined in RECIST 1.1). The status is reset and assessment continues. Please note this is different from RECIST 1.1

Thus iUPD can be assigned on multiple occasions, as long as iCPD is not declared.

Table 11 Comparison of RECIST 1.1, iRECIST and irRECIST

	RECIST 1.1	iRECIST	irRECIST
Definitions of disease: numbers, sites and target or non	Measurable are diameters greater than 10 mm (15 for nodes maximum of 5 (2 per organ))	No change from RECIST 1.1	No change from RECIST 1.1
CR, PR or SD	Cannot have met criteria for progression	Can have had iUPD (more than once) but not iCPD before iCR, iPR or iSD	Use of terminology based around RECIST 1.1
Confirmation of CR or PR	Only in non-randomized studies	As per RECIST 1.1	As per RECIST 1.1
Confirmation of SD	Not required	As per RECIST 1.1	As per RECIST 1.1
New lesions	Progression: recorded but not measured	iUPD but only becomes iCPD if on the next scan there are new lesions or the size increases by greater than 5 mm	Unclear
Confirmation of progression	Not required	Required	Required
Consideration of clinical status	Not required	Clinical stability considered at iUPD to decide treatment continuation	As iRECIST without terminology considering unconfirmed findings

Table 12 Trajectory of progression in iRECIST

Target Lesions: iCR, Non-target: iCR, no new lesions	iCR	iCR
Target lesions: iCR, Non-target: non iCR/non iUPD, no new lesions	iPR	iPR

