- For a **clinically stable** subject with first radiologic evidence of progressive disease by RECIST 1.1 (i.e., **unconfirmed progression of disease or iUPD**), it is at the discretion of the site investigator to continue treating the subject with the assigned treatment per protocol until progression of disease (iCPD) is confirmed at least 28 days from the date of the scan first suggesting PD. If radiologic progression is confirmed by subsequent scan then the subject will be discontinued from trial treatment. If radiologic progression is not confirmed by iRECIST per the site, then the patient should resume or continue trial treatment and have their next tumor imaging according to the protocol schedule of every 9 weeks (end of every 3rd treatment cycle) until progression is confirmed at a later timepoint by the site. In applying iRECIST, the appropriate documentation at

each time point must be made (i.e. iSD, iUPR, iUCR). For a more comprehensive and detailed account of the application of RECIST 1.1 and iRECIST for in-study imaging assessments please refer to the imaging guide document Note that RECIST 1.1 must always serve as the primary imaging assessment guide up to the first indication of disease progression after which iRECIST may be used as described.

- Any subject deemed **clinically unstable** should be discontinued from trial treatment at 1st radiologic evidence of PD and is not required to have repeat imaging for PD confirmation.
- In subjects who discontinue study therapy without documented disease progression, every effort should be made to continue monitoring their disease status by tumor imaging using the same imaging schedule used while on treatment (every 9 weeks), until (1) the start of new anti-cancer treatment, (2) disease progression (3) death, or (4) the end of the study, whichever occurs first.

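### Protocol Table 9 judges target lymph nodes by short axis for complete response but by longest diameter for partial response, stable disease and progression, so one nodal record can fall into two categories

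*Protocol*

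**What the plan says.** Protocol 9.1 names the criteria: "Response and progression will be evaluated in this study using Response Evaluation Criteria in Solid Tumors (RECIST) guideline version 1.1", together with iRECIST. Table 9 in section 9.1.2 then sets out the categories.

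- **Complete response:** "Any pathological lymph nodes (target or non-target) must have reduction in short axis to < 10mm". Nodes can therefore be target lesions, and the short axis decides.
- **Partial response:** at least a 30% "decrease in the sum of the longest diameter of target lesions, taking as reference the baseline sum longest diameter".
- **Stable disease:** neither PR nor PD, "taking as reference the smallest sum longest diameter since treatment started".
- **Progression:** new lesions, or a 20% or greater "increase in the sum of the longest diameter of target lesions, taking as reference the smallest sum longest diameter recorded since the treatment started".

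Table 11 (section 9.1.4) describes measurable disease as "Measurable are diameters greater than 10 mm (15 for nodes maximum of 5 (2 per organ", with no axis for the nodal figure. For target lesions that merge, section 9.1.2.2 says "the vector of the longest diameter of the now merged lesions will be recorded as the lesion measurement", again without a nodal exception. Table 10 takes a single target-lesion category as its input and does not say which prevails if Table 9 yields two.

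Section 9.1.5 points elsewhere for detail: "for in-study imaging assessments please refer to the imaging guide document". SAP 4.2.3 bases the analyses on the independent radiologist's category, with the process described in an Imaging Review Charter, and reports the clinic's category descriptively only. Neither the imaging guide nor the charter is among the documents.

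**The concern.** The four categories should rest on one measurement, so that a complete response always satisfies the rule for a partial response. Table 9 breaks this for target nodes: the CR row looks at one axis and the other three rows at another. Nothing in the protocol or SAP says that nodes enter the sum by short axis.

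The text matters first at the sites. Protocol 9.1.1 uses the local reading to determine eligibility and response. Section 9.1.5 has sites assess response and progression and make treatment decisions. Protocol 9.1.3 and SAP 4.2.3 both list site-assessed progression among the events that end RECIST 1.1 assessment. Two sites reading the same node could report different categories and both be following Table 9.

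If the central read used the same wording, the ambiguity would also reach the primary endpoint, where few responses decide each cohort.

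**Working it through.** **1. The design that uses the response count.** Table 9 states no figure to reproduce, so the check starts with the stated type I error of 0.05 and power of 0.80. Inputs are from Protocol Table 17 (also SAP Table 4). The probability of rejection at response rate p is the sum, over x1 from r1+1 to n1, of P(X1 = x1 | n1, p) x P(X2 >= r2+1-x1 | n-n1, p).

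| Cohort | n1 / n / r1 / r2 | p0, p1 | Responses to reject | Exact type I error | Exact power |
|---|---|---|---|---|---|
| Colorectal | 13 / 27 / 0 / 3 | 5%, 20% | 4 of 27 | 0.0416 | 0.8011 |
| Ovarian | 16 / 26 / 1 / 4 | 7%, 25% | 5 of 26 | 0.0306 | 0.8029 |
| Cervical | 15 / 25 / 1 / 5 | 10%, 30% | 6 of 25 | 0.0328 | 0.8017 |

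The stated power reproduces and the type I error is within 0.05. The design is sound given a well-defined response.

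**2. Table 9 applied to constructed nodal records** (short x long axis, mm). A node below 10 mm is taken not to have to vanish for CR; otherwise the nodal sentence in that row would be redundant.

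| Record | Short axis | Longest diameter |
|---|---|---|
| A: 16 x 26 to 9 x 22 | 9 < 10: CR | 22/26 - 1 = -15%: SD |
| B: A continued, to 9.5 x 27 | 9.5 < 10: CR row still met | 27/22 - 1 = +23% (+5 mm): PD |
| C: 18 x 28 plus a 30 mm lesion, to 11 x 26 plus 20 mm | (11+20)/(18+30) - 1 = 31/48 - 1 = -35%: PR | (26+20)/(28+30) - 1 = 46/58 - 1 = -21%: SD |
| D: 20 x 30 to 15 x 20 | 15/20 - 1 = -25%: SD | 20/30 - 1 = -33%: PR |

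A and B meet two rows of the printed table at once. C and D show that the choice of axis can remove a response or create one.

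**3. What a single axis repairs.** Take the 15 mm nodal size as short axis (an assumption, since Table 11 names none). A target node that starts at 15 mm or more and falls below 10 mm has shrunk by more than (15-10)/15 = 33%, which exceeds 30%. CR then implies PR, and the CR/SD conflict goes. The CR/PD overlap stays: a nodal short axis rising from a 6 mm nadir to 8 mm is +33%, and from 4 mm to 9 mm is +125% and +5 mm, yet both are still below 10 mm.

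**4. Size.** The documents give no share of nodal target disease, no lesion counts and no ratio of axis changes, so these are scenarios only.

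- Assume 2-4 target lesions per patient, mean shrinkage 30% (SD 15 points), and 200,000 simulated patients per setting. With 20% of lesions nodal and the long axis changing 70% as much as the short, 11% of short-axis PRs are not PR on longest diameter. With 35% nodal and 50%, the figure is 35%.
- With 10% nodal, or 90% concordance between axes, about 4-6% are lost.
- With both axes changing in proportion, the loss is 0% if shrinkage is drawn per patient. If it is drawn per lesion, about 2-4% move each way and nearly cancel.

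**5. Conditional effect on the test, if the central read were affected.** Missing a fraction f of true responders replaces p1 by p1(1-f). For f = 5% / 10% / 20%, power is 0.765 / 0.724 / 0.629 (colorectal), 0.761 / 0.713 / 0.602 (ovarian) and 0.754 / 0.699 / 0.571 (cervical). In the other direction, counting a fraction g of non-responders replaces p0 by p0 + g(1-p0). At g = 2%, type I error is 0.107, 0.072 and 0.065 respectively. The values of f and g are assumed.

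**The case against.** The strongest reply is that Table 9 is a summary. The protocol names RECIST 1.1 as the governing criteria and refers to an imaging guide, and the SAP takes the independent radiologist's category under a charter. Nothing shows that the central reader applies the printed shorthand. This stands, and it limits the point. A reader might infer that the primary ORR already depends on the axis, and that one nodal patient could decide a cohort. The documents do not support that unless the charter follows Table 9.

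It may also be said that site misreading does little harm. Scans continue every 9 weeks, SAP 4.2.3.1 accepts confirmation at the next 9-weekly scan, and a first site call of progression need not stop treatment in a clinically stable patient. That is fair, and a response missed at the site need not be lost. It does not remove the inconsistency, because site reads still inform treatment and site-assessed progression still closes RECIST 1.1 assessment. Naming RECIST 1.1 also does not tell a site to set aside the wording in front of it.

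Finally, the documents show inconsistency, not which axis is correct for PR and PD. That too is right. The case for short axis made here is internal: Table 9 already uses it for nodal CR, and it makes CR imply PR.

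**Conclusion.** The inconsistency is real and lies in the printed text. For target nodes, Table 9 mixes two axes, Table 11 leaves the nodal axis unstated, and no passage resolves it. It affects only patients with a nodal target lesion whose two axes change by different proportions, and misclassification can go either way.

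The established consequence is for site reads of response and progression. An effect on the primary ORR depends on a charter that cannot be seen.

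Two further inferences should be resisted. The 11-35% figure is not an estimate for this trial: it counts only lost PRs and is driven by the assumption that the long axis changes 50-70% as much as the short. Nor would a single axis settle everything, because the CR/PD overlap comes from a fixed 10 mm threshold beside a relative growth rule and needs its own precedence statement. The point is worth correcting because it touches the definition of response and costs almost nothing.

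**What to change.** - In the PR, SD and PD rows of Table 9, replace the longest-diameter sum with a sum of diameters: longest diameter for non-nodal target lesions, short axis for nodal target lesions, at baseline, nadir and follow-up alike.
- In Table 11, state the axis for the 15 mm nodal size.
- Add a precedence rule saying which category applies when a target node already below 10 mm short axis grows from its nadir but stays below 10 mm.
- Extend the same convention to merged nodal lesions in section 9.1.2.2.
- Confirm that SAP 4.2.3, the imaging guide and the Imaging Review Charter use the same rule. If the charter already fixes the axis, bring Table 9 into line with it and say so in the SAP.

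The cost is a change of table wording, a note to sites and a check against the charter. No extra imaging is needed.
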